### 9.1.3 Serious Adverse Event (SAE)

A planned hospitalization for a pre-existing condition, or a procedure required by the CIP, are not considered SAEs.

### 9.1.4 Adverse Device Effect (ADE)

An AE related to the use of a medical device used in this study.

This definition includes AEs resulting from insufficient or inadequate instructions for use, deployment, implantation, installation, or operation, or any malfunction of the medical device.

This definition includes any event resulting from the use error or from intentional misuse of the medical device.

### 9.1.5 Serious Adverse Device Effect (SADE).

## 9.2 Assessing, Recording and Reporting AEs

Safety surveillance within this study and the safety reporting both performed by the investigator, starts as soon as the subject is consented for the study. The safety surveillance and the safety reporting will continue until the last investigational visit has been performed, the subject/investigator concludes his participation into the study or the subject/investigator withdraws the subject from the study, except as otherwise specified in the CIP.

Records related to the subject's subsequent medical course must be maintained and submitted (as applicable) to the Sponsor until the event has subsided or, in case of permanent impairment, until the event stabilizes and the overall clinical outcome has been ascertained. All AEs will be monitored until they are adequately resolved. The status of the subject's condition should be documented at each visit.

AE data will be collected throughout the clinical study and will be reported to the Sponsor on a dedicated case report form through the EDC system. Reportable events to sponsor are considered:

1. ***All SAEs (whether or not the event is device and/or procedure related)***
2. ***All procedure, device and/or stimulation-related AEs (whether or not the event is considered serious)***

Device, procedure, and stimulation-related AEs are defined as follows:

## Clinical Investigational Plan

- Device-related: A malfunction or migration of any device component including leads, extensions, IPGs and accessories.
- Procedure-related: Biological reaction (hematoma, infection, pain, etc.) as a result of the surgical procedure to implant the device.
- Stimulation-related: Event known to be caused by stimulation from the device. Normally stimulation-related events resolve when the device is turned off or reprogrammed.

The investigator should report all SAEs to the Sponsor as soon as possible but no later than outlined below.

Clinical Site	Reporting timelines
All Sites	SAEs must be reported no later than 3 calendar days from the day the site personnel became aware of the event or as per the investigative site's local requirements, if the requirement is more stringent than those outlined.

The date the site staff became aware the event met the criteria of an SAE must be recorded in the source document.

The Investigator will further report the SAE to the local IRB/EC according to the institution's IRB/EC reporting requirements.

Adverse events that are not serious will be reported to the Sponsor, as soon as possible after the occurrence of the event.

Please reference Section 3 of this document for risk information and Section 9.3 for a complete list of adverse effects related to DRG Neurostimulation Systems.

For unexpected failure modes or unexpected for all AEs, the site should follow their standard reporting practices for medical device reporting (MDR). As defined in 21 CFR 803, a MDR reportable event (or reportable event) is an event that device user facilities become aware of that reasonably suggests that a device has or may have caused or contributed to a death or serious injury. A device user facility must report deaths and serious injuries that a device has or may have caused or contributed to, establish and maintain AE files, and submit summary annual reports to FDA.

The Investigator will assign degree of relatedness to the device for all SAEs and device, procedure and stimulation-related AEs based on NIH definitions as follows:

**Possibly Device/Procedure-Related:** (must meet at least **2** criteria)

- Has a reasonable temporal relationship to intervention,
- Could not readily have been produced by the subject's clinical state,
- Could not readily have been due to environment or other interventions,
- Follows a known pattern of response to intervention.

**Related to Device/Procedure:** (must meet at least **3** criteria)

- Has reasonable temporal relationship to intervention,

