### Revisions, Replacements or Explants (additional surgery)

- Revision, replacement or explant procedure
- Modify programming parameters (*if necessary*)
- Record AEs
- Schedule 1-Month safety follow-up call (if necessary)

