### **8.11 Revisions, Replacements, or Explants (Additional Surgery)**

The subject and the implanting physician will collectively make the decision about any possible revision of the device based upon what is medically safe, what is desired by the subject, and what is in the subject's best medical interests. Any system revision, replacement or explant will be recorded on the appropriate eCRFs. If the device is explanted for any reason and re-implantation is not an option, the subject will be followed for 1 month post-explant and then withdrawn from the study. Subjects who undergo a revision or replacement procedure will resume their previous follow-up schedule.

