## 10.3 Descriptive Endpoints

The following descriptive endpoints will be reported:

- Proportion of subjects with device, procedure or stimulation-related SAEs and non-SAEs among subjects who receive the permanent implant
- Proportion of subjects who have AEs related to the trial implant procedure among subjects who fail the trial neurostimulator phase
- Summary of procedure-related SAEs and non-SAEs by implanter experience
- Change from baseline to 1, 3, and 6 months post-permanent implant for overall pain intensity measured using the Visual Analog Scale (VAS)
- Change from baseline to 1, 3, and 6 months post-permanent implant for physical function measured using the PROMIS-29 Profile
- Change from baseline to 1, 3, and 6 months post-permanent implant for quality of life measured using the PROMIS Global Health Scale
- Change from baseline to 1, 3, 6 and 12 months post-permanent implant for neuropathic pain measured using the Neuropathic Pain Scale (NPS)

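### Protocol 9.2 ties procedure-related events to implant surgery only, which conflicts with the synopsis and 8.11 and leaves reporting of non-serious explant complications unclear

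*Protocol*

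**What the plan says.** Protocol section 9.2 lists two kinds of event that sites must report to the sponsor. The first is "All SAEs (whether or not the event is device and/or procedure related". The second is "All procedure, device and/or stimulation-related AEs (whether or not the event is considered serious". It then states "Device, procedure, and stimulation-related AEs are defined as follows" and gives three definitions. Device-related means malfunction or migration of a component. Stimulation-related means an event known to be caused by stimulation. Procedure-related means a biological reaction, with hematoma, infection and pain as examples, "as a result of the surgical procedure to implant the device".

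Additional surgery is handled elsewhere. Section 8.11 says "Any system revision, replacement or explant will be recorded on the appropriate eCRFs". It keeps a subject whose device is explanted without re-implantation in follow-up for one month before withdrawal. It does not mention adverse events. The synopsis entry for revisions, replacements and explants does tell sites to record adverse events, without the if-necessary qualifier attached at the other visits that list this task. It adds "Schedule 1-Month safety follow-up call (if necessary").

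Several outputs depend on the term. Protocol 10.3 and SAP 3.5.1 report "Proportion of subjects with device, procedure or stimulation-related SAEs and non-SAEs among subjects who receive the permanent implant" (with slightly different abbreviations in the SAP), together with a summary of procedure-related events by implanter experience. Protocol 10.7 repeats both in the annual progress reports. SAP 3.2 counts adverse device effects, which SAP 5.0 defines to include procedure-related non-serious events.

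**The concern.** For non-serious events, the three definitions in 9.2 are the filter for reporting. Explant surgery removes the device, so a hematoma, infection or pain that follows it is not, on the plain words, a reaction to implanting it. The protocol nevertheless expects such surgery and keeps explanted subjects under observation during the month when surgical reactions would be expected.

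One site may report a minor wound infection after explant because the synopsis says to record adverse events at that surgery. Another may leave it out because it meets no definition in 9.2. Differences between sites, and the total count, would then partly reflect how the protocol was read. The study is a condition of approval and its primary purpose is safety, so the non-serious burden of repeat surgery should be collected on one rule.

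**Working it through.** No arithmetic applies, because the point rests on a definition and a reporting rule. The check is to apply the text to each kind of surgery and then ask whether any other text settles the matter.

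**Step 1: a non-serious surgical wound reaction under 9.2.** It is not serious, so the first reportable category does not apply. It is neither a malfunction nor a migration, so it is not device-related. Surgery caused it, so it is not stimulation-related. Only the procedure definition remains.

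**Step 2: the procedure definition, by type of surgery.**

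| Surgery | Surgery to implant the device? |
|---|---|
| Trial or permanent implant | Yes |
| Revision or replacement placing a new lead or generator | Can readily be read as yes |
| Repositioning an existing lead | Arguable |
| Removing trial leads at the end of the trial | Arguable; could be seen as part of the trial procedure |
| Explant without re-implantation | No, on the literal words |

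The gap is clear for explant, arguable for two procedures, and weak where a new component goes in.

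**Step 3: whether other text settles it.**

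- Section 9.1.2 defines an adverse event broadly enough to include the procedures involved. It says what an adverse event is, while 9.2 selects which ones are reportable.
- Section 9.2 also says that non-serious events will be reported as soon as possible. That sentence sits with the timelines. If it covered every non-serious event, the second reportable category would do no work.
- The investigator's relatedness scale in 9.2 is applied to serious events and to device-, procedure- and stimulation-related events. A non-serious event must therefore already be in one of those classes to reach it.
- The CEC (Protocol 24.0) judges relatedness from case report forms and medical records. It can correct the class of a reported event, but the documents describe no route to one that the site did not report.
- The synopsis instruction points the other way from 9.2. It does not amend the definition, so the two stand in conflict.

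**Step 4: which results depend on the definition.**

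- Primary endpoint (SAP 2.3.1): all CEC-adjudicated serious events after permanent implant, related or not. No dependence.
- Secondary endpoints: patient-reported scores. No dependence.
- Pooled proportion of subjects with any related event (10.3, SAP 3.5.1): affected only for a subject whose sole related event is the unreported one.
- Procedure-only summaries and adverse device effect counts and rates (SAP 3.2): each unreported event is lost.

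**The case against.** The strongest reply is that 9.2 should not be read alone. The synopsis asks for adverse events at exactly these surgeries and allows for a one-month safety call. The general definition is broad, and 9.2 itself says that adverse event data are collected throughout the study. A sensible coordinator would probably record an explant infection. This stands to the extent that the defect is an inconsistency between instructions. A reader might infer that complications of explant simply need not be reported. The documents do not support that, because the synopsis says otherwise.

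A reader might also infer that a serious explant complication would be classed as unrelated to a procedure. That does not follow either. All serious events are reported, the relatedness criteria refer to intervention in general, and the CEC decides procedure relatedness independently.

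Two further limits are fair. The summary by implanter experience may be meant for implant procedures only, in which case leaving explant events out of it is not an undercount. And the activity table and part of the CEC section are redacted, the text of the serious-event definitions is largely absent from the public copy, and the case report forms are held separately. The form may therefore already capture the associated procedure. None of this changes the wording of the definition that sites are given.

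**Conclusion.** The point holds as an inconsistency with a simple cure. The 9.2 definition is narrower than the synopsis instruction, the post-explant follow-up and the descriptive endpoints require. Reporting of non-serious reactions to explant may vary by site. The same may happen, less certainly, for lead repositioning and trial-lead removal. Procedure-related non-serious events and adverse device effect counts may be understated.

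The size cannot be estimated from the documents, which give neither an explant rate nor a complication rate for additional surgery. It is tempting to start from the 11.8% of subjects with loss of stimulation due to lead migration in the pivotal trial (Protocol 2.0) and the 319 planned implants (Protocol 5.0): 0.118 × 319 = 37.6, or about 38 subjects. That does not give the number missing. Migration is itself device-related under 9.2, so these subjects are already in the pooled per-subject proportion, and surgery for migration may place a new lead, where the gap is weakest. Any loss falls on procedure-only summaries, on event counts, and on explanted subjects with no other related event.

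The primary endpoint is not affected. The conclusion rests on a literal reading of the definition and on sites treating 9.2 as the operative reporting rule. It merits correction because the remedy is cheap, not because the trial's main result is at risk.

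**What to change.** In Protocol 9.2, define procedure-related as *a biological reaction as a result of any surgical procedure to implant, revise, replace, reposition or remove any component of the trial or permanent system*, keeping the present examples. This brings 9.2 into line with the synopsis and with the purpose of the 8.11 follow-up. In the tables for Protocol 10.3 and SAP 3.5.1, show events after implant and events after additional surgery separately, so that the wider definition does not blur the implant result. If the adverse event form does not already identify the associated procedure, add a field for it.

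The cost is one phrase in the protocol and at most one form field. The reported procedure-related non-serious event rate may be slightly higher, which the separate tabulation makes interpretable. If subjects have already had additional surgery under the present wording, the report should say which events were collected before and after the change.

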### 9.3 Anticipated AEs

Possible risks to the subjects include both device- and procedural-based risks. Below is a list of the potential adverse effects associated with the implant and use of the Axium Neurostimulator System.

Risks associated with any surgical procedure: abscess; cellulitis; excessive fibrotic tissue; wound dehiscence; wound, local or systemic infection; wound necrosis; edema; inflammation; foreign body reaction; hematoma; seroma; thrombosis; ischemia; embolism; thromboembolism; hemorrhage; thrombophlebitis; adverse reactions to anesthesia; hypertension; pulmonary complications; organ, nerve or muscular damage; gastrointestinal or genitourinary compromise; seizure, convulsion, or changes to mental status; complications of pregnancy including miscarriage and fetal birth defects; inability to resume activities of daily living; and death.

Risks associated with system placement procedures: pain at the implant site, swelling; infection, cerebrospinal fluid (CSF) leakage, CSF fistula, epidural hemorrhage, bacterial meningitis, seroma, weakness, hematoma, tissue damage, nerve damage, sensory loss, spinal cord compression; and paralysis. Patient use of anticoagulation therapies may increase the risk of procedure-related complications, such as hematomas, which could produce paralysis.

Risks associated with the use of the system: lead migration; INS migration; allergic response or tissue reaction to the implanted system material; hematoma or seroma at the implant site; skin erosion at the implant site; persistent pain at the INS and/or lead site, extension, or lead site; radicular chest wall stimulation; disturbed urination; dysesthesia; decubitus; headache; allodynia; hyperesthesia; premature battery depletion; loss of pain relief over time; escalating pain; clumsiness; numbness; temporary muscle activation; and uncomfortable stimulation or ineffective pain control caused by random failure of the system components or battery, changes in electrode position, loose electrical connections, lead or extension insulation breaches or fractures, lead retention, and inability to achieve the desired pain relief results.

An additional risk to the subject is pain due to setting the stimulation parameters too high as a result of the placement and stimulation of the lead in the area of the DRG.

Below is a list of the potential adverse effects associated with the implant and use of the DRG Neurostimulation System with Proclaim DRG IPG:

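### Protocol 9.2 counts a non-serious event as stimulation-related only when stimulation is the known cause, a stricter test than its own possibly-related grade, so suspected events can miss grading and the descriptive related-AE endpoint

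*Protocol*

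**What the plan says.** Protocol section 9.2 names two classes of event that sites must report. The first is "All SAEs (whether or not the event is device and/or procedure related"). The second is "All procedure, device and/or stimulation-related AEs (whether or not the event is considered serious"). Definitions of the three kinds of relatedness follow:

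- **Device-related** means a component has malfunctioned or migrated.
- **Procedure-related** means a biological reaction resulting from the implant surgery.
- **Stimulation-related** is given as "Stimulation-related: Event known to be caused by stimulation from the device", with a remark that such events normally resolve when the device is switched off or reprogrammed.

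After the SAE timelines, the section adds: "Adverse events that are not serious will be reported to the Sponsor, as soon as possible after the occurrence of the event". This sentence carries no relatedness condition.

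A graded assessment comes next: "The Investigator will assign degree of relatedness to the device for all SAEs and device, procedure and stimulation-related AEs". Its lower grade is headed "Possibly Device/Procedure-Related" and needs at least two of four criteria. The upper grade needs at least three. Neither label mentions stimulation.

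The endpoint that depends on this wording is listed in Protocol 10.3 as "Proportion of subjects with device, procedure or stimulation-related SAEs and non-SAEs among subjects who receive the permanent implant". It also appears in Protocol 4.5 and in SAP 1.4.3 and 3.5.1, and Protocol 10.7 has it summarised annually in the progress report.

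**The concern.** For non-serious events, the definitions decide what enters the relatedness assessment. Two of the three carry no certainty condition. The stimulation definition does: the cause has to be known. A site that only suspects stimulation has no clear instruction to class the event as related, and without that class the event is not graded.

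The effects at issue are the ambiguous ones. Protocol 9.3 lists "radicular chest wall stimulation; disturbed urination; dysesthesia; decubitus; headache; allodynia; hyperesthesia" among the risks of using the system, together with numbness and clumsiness. In people with chronic neuropathic limb pain, several of these could plausibly have another cause, so the site may not know the cause when it decides what to report. That is a judgement about practice, not something the documents state.

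The study is a condition of FDA approval, and this proportion is one of its stated safety endpoints. A rule that loses suspected events can only move that component downward, the favourable direction. If sites resolve the wording differently, the proportion also mixes two definitions.

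**Working it through.** The plan states no figure that depends on this definition, so there is none to reproduce. The check is to follow one kind of event through the text.

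**1. Test case.** Take a non-serious new dysesthesia in an implanted subject. The system is intact, nothing has migrated, and the symptom is not a reaction to surgery.

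**2. Reporting class (9.2).** It is not an SAE, so the first class does not apply. It can enter only through the second.

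**3. Definitions (9.2).** With no malfunction or migration it is not device-related, and with no surgical reaction it is not procedure-related. Only the stimulation route is left, and that requires a known cause. If the cause is merely suspected, the event meets none of the three definitions.

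**4. Grading (9.2).** The scale applies to SAEs and to events already classed as related. The possibly-related grade is therefore reached after the known-cause test, not instead of it. For a non-serious, stimulation-only event the lower grade is nearly empty, because an event with a known cause is more than possible. By contrast, the adverse device effect definition in 9.1.4 asks only that the event be related to use of the device.

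**5. The general sentence on non-serious events (9.2).** There are two readings.

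- *Narrow.* It follows the SAE timelines and says when to report the non-serious events already made reportable. The test case stays out.
- *Broad.* It requires every non-serious event to be reported. The relatedness condition in the second reportable class would then do no work for these events. It would also fit poorly with section 9.5, which envisages complaints that do not involve an adverse event reportable under the protocol. Even so, a suspected event would still not be stimulation-related as defined, so it would be neither graded nor counted.

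**6. Adjudication.** Protocol section 24 asks the CEC to determine device and/or procedure relatedness and seriousness; stimulation is not named. SAP 3.2 summarises adverse device effects per CEC adjudication, and SAP section 5 includes stimulation-related events in that term. The visible text does not say who adjudicates stimulation, or whether possibly related counts as related in the endpoint.

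**7. Direction and size.** Let *q* be the proportion of implanted subjects with at least one non-serious event at least possibly due to stimulation. Let *s* be the share of those subjects whose events are only suspected and go uncounted.

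- Observed proportion = *q*(1 − *s*)
- Shortfall = *qs*

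The shortfall cannot be negative, which fixes the direction. Neither *q* nor *s* is in the documents. With *s* anywhere from 0 to 1, the observed value lies anywhere from *q* down to 0, so no useful number follows. For the combined related-AE proportion the loss is at most *qs*, because a subject with another counted related event remains in the numerator.

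**8. What is untouched.** SAP 2.3.1 counts all CEC-adjudicated serious events after permanent implant, related or not. The known-cause test does not enter there, and the device and procedure definitions contain no such test.

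**The case against.** The best defence is that the three definitions sort events by type (hardware, surgery, stimulation) and leave certainty to the graded scale. On that view, known means a recognised effect. The grading criteria themselves speak of a known pattern of response, and 9.2 directs sites to the list in 9.3. The section also allows adverse events generally, not only serious ones, to be classed as unrelated, which suggests that unproven events are expected to reach grading. Finally, the general sentence on non-serious events has no relatedness condition.

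This is a coherent reading, and it defeats one inference a reader might draw: that suspected non-serious stimulation effects are definitely not reportable. Section 9.2 does not settle that. But the defence has to read past the literal definition, and sites cannot be relied on to make the same choice.

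The eCRFs are held separately and parts of the SAP are blacked out, so a form instruction or counting rule may exist. A form instruction could help. A counting rule in the SAP could not recover events that were never entered.

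The endpoint is descriptive and has no hypothesis attached. That limits the weight of the point but does not remove it.

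**Conclusion.** The point stands in limited form. Section 9.2 sets a known-cause test for stimulation-related events ahead of a scale that admits possible ones, and its general sentence on non-serious events does not resolve the conflict. Suspected non-serious events that could only be due to stimulation may be left ungraded and uncounted, or handled differently between sites. The bias in that component is downward and of unknown size. The conclusion assumes that at least some sites apply the definition as written and that no unseen form instruction overrides it.

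Three stronger inferences are not supported:

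- **That the related-AE endpoint as a whole counts only near-certain cases.** All SAEs are reported whatever their cause and can be graded possibly related, and the device and procedure definitions contain no known-cause test.
- **That the result would not be comparable with the earlier IDE trial.** The possible-or-definite wording in Protocol section 2.0 concerns serious device effects, and the common events reported there are the definitely related ones.
- **That a number of lost subjects can be given.** Every input would be invented.

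The primary endpoint is unaffected.

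**What to change.** 1. **Protocol 9.2, definition.** Define stimulation-related as an event *known or suspected to be caused by stimulation (at least possibly related by the criteria below)*.
2. **Protocol 9.2, general sentence.** Say whether the sentence on non-serious events sets only the timing of reporting or requires all such events, and make the list of reportable classes agree with it.
3. **Protocol 9.2 and section 24.** Add stimulation to the labels of both relatedness grades and to the CEC's remit.
4. **SAP 3.5.1.** State that possibly related and related events both count, and show the two grades separately.

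The definition needs one sentence; the other items need short wording edits and a reminder to sites. The price is somewhat more AE forms and a slightly higher, less favourable related-AE proportion. Showing the grades separately lets a reader see how much of that proportion comes from suspected events.
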